1.9 DEVICE INFORMATION

1.9.1 Motion Sensor - 10-axis Bluetooth Gyro Inclinometer

The motion sensor is the “10-axis Bluetooth Gyro Inclinometer” by Wit Motion and is marketed for “rehabilitation exercises, workplace injury prevention, patient care, and healthy shortrange wireless motion measurements.” The sensor is 2.02”x1.41”x0.59” and contains a rechargeable 3.7V Li-batter with a working time of approximately 4 hours. The casing is “indoor/outdoor, waterproof, dustproof, anti-UV and vibration resistant.” The data output includes 3 axis (acceleration, gyro, angle, magnetic, and quaternion) and 1-axis barometer, air pressure, height data. Data is transmitted via Bluetooth 2.0. The device is not being studied for safety and effectiveness but is, rather, a tool for collecting basic physiologic data.

1.9.2 Incentive Spirometer - Teleflex Medical

An incentive spirometer is a device that measures the volume of the air inhaled into the lungs during inspiration. When breathing in through a volume-oriented incentive spirometer, a piston rises inside the device and measures the volume of the inspired air. The incentive spirometry device is widely used in physical, speech, and respiratory therapy as it encourages the patient to perform a slow and deep inspiration through visual feedback.[\[16\]](#) The incentive spirometer is FDA approved and will be used on label to collect physiological data and not evaluated for safety and efficacy or diagnostic purposes in support of labeling changes. The specific spirometer used for this study is the Hudson RCI 2500 VOLDYNE Volumetric Exerciser (REF 8884719011) manufactured by Teleflex Medical (Morrisville, NC USA).

STUDY POPULATION

1.10 INCLUSION CRITERIA

In order to be eligible to participate in this proof-of-concept study, an individual must meet all the following criteria:

1. Provision of signed and dated informed consent form.
2. Stated willingness to comply with all study procedures and availability for the duration of the study.
3. Male or female sex, aged 18-100
4. Ability of subject to understand and the willingness to sign a written informed consent document.

1.11 EXCLUSION CRITERIA

An individual who meets any of the following criteria will be excluded from participation in this study:

1. Pregnancy.
2. Known allergic reactions to adhesive.
3. Patients with an altered mental status that precludes understanding and consenting for the procedure and compliance with the study activities.
4. Patients with known pulmonary conditions including pulmonary fibrosis, asthma, COPD, or chronic bronchitis.

1.12 INCLUSION OF VULNERABLE PARTICIPANTS

The study is designed to recruit healthy volunteers and we will not be including incapacitated adults.

1.12.1 Participation of NIH Staff or family members of study team members

NIH staff and family members of study team members may be enrolled in this study as this population meets the study entry criteria. NIH staff will not be recruited by their principal investigator or superior. Neither participation nor refusal to participate as a subject in the research will have an effect, either beneficial or adverse, on the participant's employment or position at NIH.

Every effort will be made to protect participant information, but such information may be available in medical records and may be available to authorized users outside of the study team in both an identifiable and unidentifiable manner.

The *NIH Frequently Asked Questions (FAQs) for Staff Who are Considering Participation in NIH Research* will be made available. Please see section [**1.34.3**](#) for consent of NIH Staff.

1.13 INCLUSION OF PREGNANT WOMEN, FETUSES OR NEONATES

This study will not include pregnant women. Women will be screened verbally for pregnancy and asked to sign a clause on the consent document attesting to being not pregnant. Pregnancy causes changes in breathing given added pressure on abdomen + diaphragm. As such, their data would likely skew data analysis with an N=30.

1.14 LIFESTYLE CONSIDERATIONS

Not applicable.

1.15 SCREEN FAILURES

Screen failures are defined as participants who consent to participate in the clinical study but are not subsequently entered in the study. A minimal set of screen failure information is required to ensure transparent reporting of screen failure participants, to meet the Consolidated Standards of Reporting Trials (CONSORT) publishing requirements and to respond to queries from regulatory authorities. Minimal information includes demography, screen failure details, eligibility criteria, and any serious adverse event (SAE).

Individuals who do not meet the criteria for participation in this study (screen failure) may be rescreened. Rescreened participants should be assigned the same participant number as for the initial screening.

1.16 STRATEGIES FOR RECRUITMENT AND RETENTION

Healthy adults of both sex, races, and ethnicities at the NIH will be recruited for participation in the study. The NIH will be the only study site included. We anticipate recruitment of approximately 30 volunteers. Volunteers will be made aware of this study through word of mouth and through the assistance from the Office of Patient Recruitment. Peer recruitment is proposed as an optimal method for our preliminary proof-of-concept study on the basic physiology of breathing given its small scale, lack of PII, short duration, and lack of invasive procedures. More robust recruitment of a broader population could be accomplished under a

Abbreviated Title: Wearable Incentive Spirometry

Version Date: 09/08/2025

future protocol if the findings of this proof-of-concept study is successful. Recruitment will be conducted on a peer-to-peer level with no individuals being recruited by an individual at a higher level of authority. Additionally, all peer recruiting activities will be structured to safeguard against risks such as undue pressure or the accidental disclosure of private health information, ensuring the protection and voluntary participation of all involved.

1.16.1 Costs

There will be no cost associated with participation.

1.16.2 Compensation

No compensation will be provided to the subjects. Research results will be made publicly available at the conclusion of this study.

STUDY INTERVENTION(S) OR EXPERIMENTAL MANIPULATION(S)

1.17 STUDY INTERVENTIONS(S) OR EXPERIMENTAL MANIPULATIONS(S) ADMINISTRATION

1.17.1 Study Intervention or Experimental Manipulation Description

All participants will be included in the interventional or experimental group for this study. There is no control group. The intervention includes the application of a small motion sensor placed on the patient's chest at approximately the level of the 9th and 10th ribs at approximately the mid-axillary line using hypoallergenic double-sided adhesive tape. With the motion sensor in place, the participant will then take breaths through a traditional FDA approved incentive spirometer. They will ideally complete three breaths at each of the following volumes: 250mL, 500mL, 750mL, 1000mL, 1500mL, 2000mL, and 2500mL. Upon completion, the motion sensor will be removed, and the participant will be free to go with no future scheduled appointments or follow-up.

1.17.2 Administration

Refer to section **1.17.1** for more details.

1.18 FIDELITY

1.18.1 Interventionist Training and Tracking

N/A.

1.19 MEASURES TO MINIMIZE BIAS: RANDOMIZATION AND BLINDING

Participants will not be randomized or blinded for this proof-of-concept study.

1.20 STUDY INTERVENTION/EXPERIMENTAL MANIPULATION ADHERENCE

N/A.

1.21 CONCOMITANT THERAPY

Not applicable.

1.21.1 Rescue Therapy

N/A

Abbreviated Title: Wearable Incentive Spirometry

Version Date: 09/08/2025

STUDY INTERVENTION/EXPERIMENTAL MANIPULATION DISCONTINUATION AND PARTICIPANT DISCONTINUATION/WITHDRAWAL

1.22 DISCONTINUATION OF STUDY INTERVENTION/EXPERIMENTAL MANIPULATION

Given the nature and design of this study (lasting approximately 10-30 minutes), discontinuation from the study intervention (the motion sensor) will mean discontinuation from the study. If any partial motion data or recorded demographic data have been collected prior to decision to discontinue the intervention, it will be shredded or deleted.

1.23 PARTICIPANT DISCONTINUATION/WITHDRAWAL FROM THE STUDY

Participants are free to withdraw from participation in the study at any time upon request.

An investigator may discontinue or withdraw a participant from the study for the following reasons:

- If the participant meets an exclusion criterion (either newly developed or not previously recognized) that precludes further study participation
- If the participant repeatedly fails to show up to their appointment
- Screen Failure

The reason for participant discontinuation or withdrawal from the study will be recorded on the Case Report Form (CRF).

1.24 LOST TO FOLLOW-UP

There will be no follow-up associated with this study.

STUDY ASSESSMENTS AND PROCEDURES

1.25 SCREENING PROCEDURES

1.25.1 Screening activities performed prior to obtaining informed consent

Minimal risk activities that may be performed before the subject has signed a consent include the following:

- Email, written, in person or telephone communications with prospective subjects.

1.25.2 Screening activities performed after a consent for screening has been signed

N/A

1.26 STUDY EVALUATIONS & PROCEDURES

All patients consented for participation will undergo the following procedures:

1. Recording self-reported age, sex, height, and weight.
2. Application of the motion sensor using a medical grade double sided adhesive.
3. While seated, each participant will ideally take three breaths at each of the following volumes through a traditional FDA approved incentive spirometer: 250mL, 500mL, 1000mL, 1500mL, 2000mL, and 2500mL. The participants will hold each breath for approximately 5 seconds before exhaling.
4. Data collection will include motion data transmitted from the motion sensor to a secure NIH server.

Abbreviated Title: Wearable Incentive Spirometry

Version Date: 09/08/2025

None of this data will be transmitted back to the participants themselves. All findings associated with this study will, however, be made publicly available upon the completion of this study.

1.26.1 Biospecimen Evaluations

N/A.

1.26.2 Samples for Genetic/Genomic Analysis

N.A.

1.27 SAFETY ASSESSMENTS

All participants will be verbally screened for pregnancy and a history of skin allergy to adhesives to reduce risk of adverse effects.

1.28 ADVERSE EVENTS AND SERIOUS ADVERSE EVENTS

1.28.1 Definition of Adverse Event

Adverse event means any untoward medical occurrence associated with the use of an intervention in humans, whether or not considered intervention-related (21 CFR 312.32 (a)).

1.28.2 Definition of Serious Adverse Events (SAE)

An adverse event or suspected adverse reaction is considered "serious" if, in the view of either the investigator or sponsor, it results in any of the following outcomes: death, a life-threatening adverse event, inpatient hospitalization or prolongation of existing hospitalization, a persistent or significant incapacity or substantial disruption of the ability to conduct normal life functions, or a congenital anomaly/birth defect. Important medical events that may not result in death, be life-threatening, or require hospitalization may be considered serious when, based upon appropriate medical judgment, they may jeopardize the participant and may require medical or surgical intervention to prevent one of the outcomes listed in this definition. Examples of such medical events include allergic bronchospasm requiring intensive treatment in an emergency room or at home, blood dyscrasias or convulsions that do not result in inpatient hospitalization, or the development of drug dependency or drug abuse.

1.28.3 Classification of an Adverse Event

1.28.3.1 Severity of Event

For adverse events (AEs) not included in the protocol defined grading system, the following guidelines will be used to describe severity.

- **Mild** – Events require minimal or no treatment and do not interfere with the participant's daily activities.
- **Moderate** – Events result in a low level of inconvenience or concern with the therapeutic measures. Moderate events may cause some interference with functioning.
- **Severe** – Events interrupt a participant's usual daily activity and may require systemic drug therapy or other treatment. Severe events are usually potentially life-threatening or incapacitating. Of note, the term "severe" does not necessarily equate to "serious".]

1.28.3.2 Relationship to Study Intervention/Experimental Manipulation

All adverse events (AEs) will have their relationship to study procedures, including the intervention, assessed by an appropriately trained clinician based on temporal relationship and his/her clinical judgment. The degree of certainty about causality will be graded using the categories below.

Related – The AE is known to occur with the study procedures, there is a reasonable possibility that the study procedures caused the AE, or there is a temporal relationship between the study procedures and the event. Reasonable possibility means that there is evidence to suggest a causal relationship between the study procedures and the AE.

Not Related – There is not a reasonable possibility that the study procedures caused the event, there is no temporal relationship between the study procedures and event onset, or an alternate etiology has been established.

1.28.3.3 Expectedness

A clinician with appropriate expertise in allergic dermatitis will be responsible for determining whether an adverse event is expected or unexpected. An AE will be considered unexpected if the nature, severity, or frequency of the event is not consistent with the risk information previously described for the study procedures.

1.28.4 Time Period and Frequency for Event Assessment and Follow-Up

The occurrence of an adverse event or serious adverse event (SAE) may come to the attention of study personnel during study visits and interviews of a study participant presenting for medical care, or upon review by a study monitor.

All AEs, not otherwise precluded per the protocol, will be captured on the appropriate case report form (CRF). Information to be collected includes event description, time of onset, clinician's assessment of severity, relationship to study procedures (assessed only by those with the training and authority to make a diagnosis), and time of resolution/stabilization of the event. All AEs occurring while on study will be documented appropriately regardless of relationship. All AEs will be followed to adequate resolution.

Any medical or psychiatric condition that is present at the time that the participant is screened will be considered as baseline and not reported as an AE. However, if the study participant's condition deteriorates at any time during the study, it will be recorded as an AE.

Changes in the severity of an AE will be documented to allow an assessment of the duration of the event at each level of severity to be performed. Documentation of onset and duration of each episode will be maintained for AEs characterized as intermittent.

The research coordinator will record events with start dates occurring any time after informed consent is obtained until 7 (for non-serious AEs) or 30 days (for SAEs) after the last day of study participation. At each study visit, the investigator will inquire about the occurrence of AE/SAEs since the last visit. Events will be followed for outcome information until resolution or stabilization.

1.28.5 Adverse Event Reporting

In consultation with the PI, a trained member of the study team will be responsible for conducting an evaluation of all adverse events and shall report the results of such evaluation to the NIH Institutional Review Board (IRB) as per [Policy 801](#).

1.28.6 Serious Adverse Event Reporting

In consultation with the PI, a trained member of the study team will be responsible for conducting an evaluation of a serious adverse event and shall report the results of such evaluation to the Sponsor and the NIH Institutional Review Board (IRB) as per [Policy 801](#).

1.28.7 Events of Special Interest

N/A.

1.28.8 Reporting of Pregnancy

N/A.

1.29 UNANTICIPATED PROBLEMS

1.29.1 Definition of Unanticipated Problems

Any incident, experience, or outcome that meets all of the following criteria:

- Unexpected in terms of nature, severity, or frequency given (a) the research procedures that are described in the protocol-related documents, such as the Institutional Review Board (IRB)-approved research protocol and informed consent document; and (b) the characteristics of the participant population being studied; and
- Related or possibly related to participation in the research (“possibly related” means there is a reasonable possibility that the incident, experience, or outcome may have been caused by the procedures involved in the research); and
- Suggests that the research places participants or others (which may include research staff, family members or other individuals not directly participating in the research) at a greater risk of harm (including physical, psychological, economic, or social harm) than was previously known or expected.

1.29.2 Unanticipated Problem Reporting

The investigator will report unanticipated problems (UPs) to the NIH Institutional Review Board (IRB) as per [Policy 801](#).

STATISTICAL CONSIDERATIONS

1.30 STATISTICAL HYPOTHESIS

- Primary Endpoint Hypothesis: We will be able to transmit waveform data corresponding to each breathing exercise from the wearable motion sensor to the secure NIH database.
- Secondary Endpoint Hypothesis: Chest wall motion harnessed by a wearable motion sensor can be accurately converted to volume of inspiration.

1.31 SAMPLE SIZE DETERMINATION

We hope to recruit approximately 30 participants for initial proof-of-concept data collection.

1.32 POPULATIONS FOR ANALYSES

All participants will be analyzed via a per-protocol analysis. This method defines a subset of the participants in the full analysis (ITT) set who complied with the protocol sufficiently to ensure that these data would be likely to a) result in accurate models to predict post-operative outcomes, and b) represent the effects of the wearable on post-operative outcomes.

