The trial will be carried out in accordance with International Council on Harmonisation Good Clinical Practice (ICH GCP) and the following:

- United States (US) Code of Federal Regulations (CFR) applicable to clinical studies (45 CFR Part 46, 21 CFR Part 50, 21 CFR Part 56, 21 CFR Part 312, and/or 21 CFR Part 812)

National Institutes of Health (NIH)-funded investigators and clinical trial site staff who are responsible for the conduct, management, or oversight of NIH-funded clinical trials have completed Human Subjects Protection and ICH GCP Training.

The protocol, informed consent form(s), recruitment materials, and all participant materials will be submitted to the Institutional Review Board (IRB) for review and approval. Approval of both the protocol and the consent form must be obtained before any participant is enrolled. Any amendment to the protocol will require review and approval by the IRB before the changes are implemented to the study. In addition, all changes to the consent form will be IRB-approved; an IRB determination will be made regarding whether a new consent needs to be obtained from participants who provided consent, using a previously approved consent form.

PROTOCOL SUMMARY

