1.1 SYNOPSIS

Title:	Feasibility of Measuring Volume of Inspiration Via Non-Invasive Motion Sensors
Study Description:	This protocol is a basic physiologic proof-of-concept study enrolling normal volunteers to determine the feasibility of measuring volume of inspiration from chest wall motion measured via non-invasive thoracic motion sensors. The motion sensors are not medical devices because they are not intended to diagnose a disease or condition or to cure, mitigate, treat or prevent disease. Since motion sensors are not being evaluated for diagnostic purposes or being studied themselves within the context of this protocol and are only intended to collect physiological data, they are not to be considered investigational. The data collected in this feasibility study will not contain any personally identifiable information (PII). In this study, healthy participants will complete a total of approximately 18 measured breaths through a traditional incentive spirometer while wearing small, non-invasive motion sensors on their thorax at approximately the level of the 9 th and 10 th ribs unilaterally or bilaterally. The incentive spirometer is an FDA approved medical device. This study does not aim to study the safety or effectiveness of this device but rather utilize the device as a tool to measure volume of inspiration. The waveform data collected from the devices with each breath will then be analyzed with the intention to develop an algorithm that could convert chest wall motion to a discrete volume of inspiration in real time. Total enrollment time will be about 10-30 minutes per participant.
Objectives:	
Primary:
 
To collect chest wall motion data corresponding to various volumes of inspiration from a non-invasive wearable device.
 
Secondary:
 
To develop an algorithm which can convert chest wall motion to volume of inspiration and assess the algorithm using cross-validation strategy.

Endpoints:	
Primary:
 
A database of motion waveforms corresponding to each measured volume of inspiration via traditional incentive spirometer.
 
Secondary:
 
A cross-validated algorithm that converts chest wall motion to volume of inspiration.

Study Population:	Healthy volunteers of both sex and demographic groups who are ages 18 and older.

Abbreviated Title: Wearable Incentive Spirometry

Version Date: 09/08/2025

[figure not shown]

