Description of Sites/Facilities Enrolling Participants: All participants will be healthy volunteers recruited at the NIH.

Study Duration: 1 month

Participant Duration: 15-30 minutes

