1.5 OVERALL DESIGN

Healthy volunteers (n = 30) will be recruited for participation in this proof-of-concept study. Each participant will be consented and assigned a study number to ensure that all data is non-PII. Participants will be asked to fill out a de-identified form with their age, sex, height and weight prior to application of motion sensor (see section **1.6**).

Each participant will wear the devices for approximately 10-30 minutes while they perform a series of breathing exercises. The thoracic wearable will be adhered unilaterally or bilaterally at approximately the level of the 9th and 10th ribs at the mid-axillary line. Hypoallergenic double-sided tape will be used to adhere the motion sensor to the volunteers' torso in this position. The participant will ideally take three breaths through a traditional incentive spirometer while wearing the devices at each of the following volumes: 250mL, 500mL, 1000mL, 1500mL, 2000mL, and 2500mL. Each breath will be held for approximately 5 seconds before being released. Throughout this period, the thoracic wearable will be detecting chest wall expansion. All data will be transmitted to a secure server located within the NIH clinical center for analysis and model creation. Upon completion of the breathing exercises, the device will be removed from the participant, and the participant will be free to leave. There will be no further study visits or contact required.

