1.7 JUSTIFICATION FOR INTERVENTION

The entire duration of study participation is 10-30 minutes, making this an incredibly low-commitment study for healthy volunteers. Minimum acceptable study participation is completion of the demographic information at least one attempt of all measured lung volumes, as it is possible that some participants will not be capable of taking the maximal volume of inspiration.

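### Section 1.32 selects the analysis set by post-operative criteria that a single session in healthy volunteers cannot supply

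*Combined protocol and SAP*

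**What the plan says.** Section 1.32 opens with "All participants will be analyzed via a per-protocol analysis". Its next sentence describes something narrower: a subset of a full analysis (ITT) set, namely participants who "complied with the protocol sufficiently to ensure that these data would be likely to a) result in accurate models to predict post-operative outcomes". Criterion (b) then asks that the same data should "represent the effects of the wearable on post-operative outcomes". No other section defines an ITT set or states a per-protocol criterion.

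The rest of the document describes a study without such outcomes. The Synopsis states: "All participants will be healthy volunteers recruited at the NIH". Section 1.5 adds: "There will be no further study visits or contact required", and section 1.24 rules out follow-up. Section 1.26 collects self-reported age, sex, height and weight, plus motion data during the spirometer breaths. The secondary endpoint in section 1.33.3 is an algorithm for inspired volume.

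The protocol does hold a participation rule based on records. Section 1.7 says: "Minimum acceptable study participation is completion of the demographic information at least one attempt of all measured lung volumes". Section 1.8 defines completion in much the same way, with the sensor in place. Section 1.32 refers to neither.

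**The concern.** The analysis set decides whom the algorithm's accuracy (sections 1.33.1 and 1.33.3) and the sex and BMI comparisons (section 1.33.5) describe. If its criteria cannot be assessed from study data, the word sufficiently is left to judgement. Two analysts could then form different sets from the same records, and a reader of the results could not tell which was used.

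The type of criterion is a second difficulty. Criterion (a) asks whether a participant's data are likely to yield an accurate model. Even with the outcome corrected to inspired volume, admitting people on that basis and then reporting accuracy in those admitted would be circular.

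**Working it through.** The plan gives no figure to reproduce, so the check is mainly a comparison of sections.

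| Needed to apply section 1.32 | What the plan provides |
|---|---|
| Participants who have had surgery | Healthy volunteers (1.1) |
| Time in which a post-operative outcome could occur and be seen | One session of 10 to 30 minutes, no later visits or follow-up (1.5, 1.24) |
| A recorded post-operative outcome | Age, sex, height, weight and motion data (1.26) |
| A model of that outcome | A model of inspired volume (1.33.3) |
| A defined ITT set to take the subset from | The term is used in 1.32 and not defined |

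Post-operative use appears only as background (1.3) and possible future benefit (1.4.2).

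**Search for a rule elsewhere that would fill the gap.**
- The deviation classes in 1.42.1.1 are not tied to an analysis set.
- The quality checks in 1.33.1 and 1.33.2 remove waveforms, not participants.
- The clinical labels in 1.33.1 and the chart data in 1.41.1 name no post-operative outcome.
- The adverse-event windows in 1.28.4 are not post-operative follow-up.
- Sections 1.7 and 1.8 would serve, but 1.32 does not cite them.

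**Two hypothetical records show that the ambiguity has content.**
- A participant keeps the sensor on to the end, never attempts the largest volume, and has clean waveforms for the others. The opening sentence of 1.32 includes this person and the 1.7/1.8 rule does not. Criteria (a) and (b) give no answer. Section 1.22 does not delete the data, because the intervention was not discontinued.
- A participant attempts every volume, but every waveform is removed as corrupted. This person is a completer under 1.8 and contributes nothing to the algorithm.

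**Scale of one exclusion.** Six volumes × 3 breaths = 18 per participant, which agrees with the Synopsis: "healthy participants will complete a total of approximately 18 measured breaths through a traditional incentive spirometer". With 30 participants, 18 × 30 = 540 planned breaths. One participant is 1/30 = 3.3% of the sample and up to 18/540 = 3.3% of the breaths.

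**The completion rule has its own loose end.** It requires an attempt at every volume. Sections 1.2, 1.5 and 1.26 list six volumes. Section 1.17.1 lists seven, adding 750 mL: 7 × 3 = 21 breaths per participant and 21 × 30 = 630 in total. The rule cannot be applied uniformly until these sections agree.

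**The case against.** The best defence is that little can diverge in practice. The session is short, completion is defined in 1.7 and 1.8, and section 1.22 treats stopping as leaving the study and destroys partial data. The retained set is therefore probably close to the completers. The study is also a proof of concept without an accuracy threshold, and section 1.8 places any larger study under a new protocol. This limits the practical consequence, and it stands. It does not repair section 1.32, which is not linked to any of those sections and remains the operative definition.

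Four stronger readings are tempting, and the documents do not support them:

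- A reader might infer that the plan lets analysts drop poorly fitting participants once model error is known. The wording looks forward, concerns models of post-operative outcomes, and sets no timing. Such exclusion is not ruled out, but that rests on silence.
- A reader might infer that the volume discrepancy would turn every completer into a non-completer. This would require running sessions on one list and judging them on the other. Sections 1.2, 1.5 and 1.26 and the breath count in 1.1 all fit six volumes, and 1.7 speaks of volumes that are measured.
- A reader might infer that the primary endpoint's denominator is undermined, because 1.33.2 asks for transmission from all participants while 1.22 deletes some data. Discontinuation is an exit from the study, so those remaining is a fair reading, and the endpoint is a database, not a proportion.
- A reader might infer that exclusions unrelated to error would be harmless to the accuracy estimate. The model is trained and cross-validated on the same participants, so a smaller set can itself change held-out error.

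**Conclusion.** The point holds. Section 1.32 states a selection rule that this study cannot apply, sets it beside a sentence that includes everyone, and takes its subset from a set that is not defined. This is a rule that is wrong as written, not a missing detail, and it should be fixed before the data are analysed.

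The effect on reported accuracy cannot be sized: the documents give no exclusion rate, no error measure and no accuracy threshold. The only scale available is 3.3% of the sample per excluded participant, assuming that the approximate target of 30 is met. The held-out test set in 1.33.3 bars parameter optimization there, but it does not govern who enters the data. The conclusion rests on the text of the sections compared above and on no statistical assumption.

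**What to change.** In section 1.32, delete criteria (a) and (b) and the reference to an ITT set. Then:

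1. Define one set for the algorithm and the sex and BMI analyses: all enrolled participants who did not discontinue under 1.22 and who have at least one waveform retained after the quality check in 1.33.1. Use the 1.7/1.8 completion rule as a sensitivity set if it gives a different group. The main set is deliberately wider than that rule, so that usable breaths are kept from someone who stays but misses a volume.
2. Decide participant and waveform exclusions from procedure records and signal quality alone, before any model error is seen.
3. Report the numbers of participants and waveforms excluded, with reasons, and the number of participants who discontinued, with the reason that section 1.23 already places on the CRF.
4. Reconcile the six-volume list (1.2, 1.5, 1.26) with the seven-volume list (1.17.1), so that the completion rule has one meaning.

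The cost is a short amendment and a small exclusions table. The Statement of Compliance applies: "Any amendment to the protocol will require review and approval by the IRB before the changes are implemented to the study". No further measurements on participants are needed for the analysis set. Reported accuracy could turn out less favourable.
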